After completing the 10-day CGM session, the sensor will be removed by a trained study staff member. To remove the sensor, the adhesive patch will be gently peeled off from the skin. Removal of the sensor is a painless procedure. The sensor/transmitter will be discarded after use. CGM removal will occur during Visit 3.

Hyperinsulinemic-euglycemic clamp (Visit 3): After an overnight fast, eligible subjects will return to the YNHH HRU. Two IV catheters will be inserted: one into a distal arm or hand vein that will be placed in a heated box to allow for the sampling of arterialized venous blood; the second into an antecubital vein for administration of a primed (200 mg/m^2) and continuous infusion of [6,6-2H] Glucose and [2H5] Glycerol

(non-radioactive stable isotopes) as well as for collecting blood samples for insulin and glucose measurements. After an equilibration period lasting 2 hours., the 2-step euglycemic-hyperinsulinemic clamp study will be performed. A primed-continuous infusion of regular insulin will be given at 8 mU/(m^2 × min) during the first 2 hours, and increased to 40 mU/(m^2 × min) for the subsequent 2 hours. Plasma glucose levels will be measured every 5 min, and a variable glucose infusion will be initiated to maintain levels at ~90 mg/dl. Plasma samples will be drawn at baseline and throughout the infusion period for measurement of isotope enrichment, insulin, NEFA, glycerol turnover, and additional hormones which may be altered with lactation. Approximately 160 mL of blood will be drawn at this visit.

Also at this visit, we will perform indirect calorimetry a total of 3 times (once before and twice during the insulin clamp). A transparent plastic hood will be placed over the participant's head for 30 minutes each time. A hose connects the hood to a calorimeter, which measures oxygen consumption and carbon dioxide production and calculates resting energy expenditure.

After the insulin clamp is completed, body composition will be assessed using whole body DXA. The DXA scan will be performed in the HRU to measure fat distribution, body fat, lean body mass and bone density.

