### 13. Statistical Considerations: Describe the statistical analyses that support the study design.

Group sample sizes of 15 and 15 achieve 80% power to detect a between-group difference of 0.61 in a design with 7 repeated measurements (taken at time 0, 5, 10, 30, 60, 90, 120 min) having a autoregressive AR(1)

covariance structure when the standard deviation is 1, the correlation between observations on the same subject is 0.6, and the alpha level is 0.05. To account for up to 5-10% missing data due to drop out or poor quality data, we will need to enroll a total of 32 subjects (16 per group) for this study. Data Analysis: Primary endpoints: Whole body insulin sensitivity, endogenous glucose production, whole body lipid turnover rates. Secondary endpoints: Plasma NEFA, TGs, insulin levels, metrics of body composition. Statistical Analysis: Before statistical testing, all continuous variables will be tested for normality of distribution. Summary statistics will be computed. For between-group comparisons of patient characteristics, two sample t-test or Mann-Whitney U test will be used for continuous variables, and Fisher's exact test for categorical variables. Comparisons of repeatedly measured glucose and lipid turnover rates will be made using the mixed model analysis. Fixed factors include group and time and their interactions. A random effect for subject plus an autoregressive covariance matrix will be used to accommodate within-subject correlation of repeated assessments. Linear contrasts comparing differences between groups or different time points within a group will be estimated.

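### The 80% power is computed for seven values over 0–120 min, a grid that does not match the 4-hour two-step clamp that supplies the primary endpoints

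*Combined protocol and SAP*

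**What the plan says.** Section I, item 13 (Statistical Considerations) states: "Group sample sizes of 15 and 15 achieve 80% power to detect a between-group difference of 0.61". The design assumed is "7 repeated measurements (taken at time 0, 5, 10, 30, 60, 90, 120 min", with an AR(1) "covariance structure when the standard deviation is 1" and "the correlation between observations on the same subject is 0.6, and the alpha level is 0.05". It does not say which procedure the times belong to, what time 0 is, or whether the test is one- or two-sided.

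The same item lists "Primary endpoints: Whole body insulin sensitivity, endogenous glucose production, whole body lipid turnover rates". Turnover rates are to be compared in a mixed model with group, time and their interaction. Contrasts between groups or between time points are foreseen, but none is named as primary.

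Section I, item 4 (Research Plan, Visit 3) describes a 2-hour tracer equilibration followed by insulin at 8 mU/(m² × min) "during the first 2 hours, and increased to 40 mU" per m² per min for 2 more hours. Plasma glucose is read every 5 min. Samples for isotope enrichment, insulin, NEFA and glycerol turnover are drawn at baseline and during the infusions, without clock times.

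**The concern.** A power figure is useful only if the quantity it describes is the one that will be tested. Here the assumed measurement times stop at 120 min, while insulin runs for 240 min at two rates. Insulin sensitivity and suppression of glucose production are normally read at steady state within a step, yet the plan sets no such window for either step.

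Two things are at stake. First, the 80% may not apply to any of the three primary endpoints. Second, with no window and no named contrast, the comparison that decides each endpoint could be chosen after the data are seen.

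**Working it through.** **Step 1: place the grid on the Visit 3 timeline.** Insulin runs for 120 + 120 = 240 min, after 120 min of equilibration.

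| Reading of time 0 | What the grid covers | What it leaves out |
|---|---|---|
| Start of insulin | First step (120 min is the boundary) | Second step: 0 of 7 times within it |
| Start of the second step | Second step | First step |
| Start of the tracer | Equilibration | Both insulin steps |
| OGTT (Visit 1, whose times are also not listed) | A different procedure | The whole clamp |

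Repeating the grid in each step would give 13 distinct times, not the seven that were assumed.

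**Step 2: reproduce the plan's figure.** Inputs from item 13: n = 15 per group, difference 0.61, SD 1, ρ = 0.6, α = 0.05. Take the lag as the measurement number. The variance of the mean of seven values is

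v = (1/49) × [7 + 2 × Σ (7 − k) × 0.6^k], k = 1 to 6

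The sum is 3.6 + 1.8 + 0.864 + 0.3888 + 0.1555 + 0.0467 = 6.855, so v = (7 + 13.710)/49 = 0.4227.

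The standard error of the group difference is √(2 × 0.4227/15) = 0.2374, and 0.61/0.2374 = 2.57. With 28 degrees of freedom, the t power is:

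- one-sided: 80.6%, detectable difference 0.605
- two-sided: 69.9%, detectable difference 0.689

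Optimal (GLS) weighting gives v = 0.4000, with t power of 82.4% one-sided and 72.2% two-sided. If the lag is counted in real minutes, 80% two-sided (normal approximation) arises only if ρ = 0.6 applies to an unstated lag of about 13 min (equal weights) or 16 min (GLS). The stated figure is therefore consistent with a one-sided test of the group difference averaged over the seven times.

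**Step 3: weight of the first 10 min in that average.** Equal weights give 3/7 = 42.9%. GLS with lag by measurement number gives 0.25 + 0.10 + 0.10 = 45%. GLS in real time, assuming ρ = 0.6 per 20 min, gives about 30%.

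**Step 4: power for one value per woman in a window.** Here v = 1, the standard error is √(2/15) = 0.3651, and 0.61/0.3651 = 1.67. The t power is 36.4% two-sided and 49.4% one-sided. The two-sided detectable difference is 1.06 SD (1.02 by the normal approximation).

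**Step 5: power when four samples in one 30-min window are averaged.** The documents give no such sampling, so 10-min spacing is an assumption.

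- ρ = 0.6 between successive samples: v = [4 + 2 × (3 × 0.6 + 2 × 0.36 + 0.216)]/16 = 0.592. Two-sided power is 58.4% (normal) or 55.4% (t).
- ρ = 0.6 per 20 min: v = [4 + 2 × (3 × 0.7746 + 2 × 0.6 + 0.4648)]/16 = 0.749. Two-sided power is 48.8% (normal) or 46.2% (t).

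**The case against.** The grid appears once, in the power sentence. Nothing makes it the clamp draw schedule or the time points of the mixed model. Visit 3 samples throughout both insulin steps, and the model's interaction term and contrasts allow a comparison at any chosen time. Aim 1 also has a feasibility goal, so modest power need not disqualify the study. All of this stands, and it rules out two stronger readings.

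A reader might infer that the high-insulin response is not measured. The Visit 3 text contradicts that: the second step is sampled. What it lacks is a place in the power design and a defined window.

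A reader might also infer that the early values dilute the effect. For example, with insulin action rising to plateau with a half-time of 30 min, a 0.61 SD plateau difference would appear as about 0.29 SD in the seven-point mean. The documents do not support that figure. The half-time comes from outside them. The calculation sets the group difference to zero at time 0, although glucose production and lipid turnover can already differ at fasting under the protocol's own hypothesis. It also treats 0.61 as a plateau difference, which item 13 does not say. Dilution of the insulin-stimulated difference would arise only if the group effect averaged over this grid were the analysis, and the plan never names that effect as primary.

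None of this rescues the power figure. No reading in the table covers both steps, and the 5-min schedule is for plasma glucose, not for the tracer samples that the turnover endpoints need.

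**Conclusion.** The mismatch is real. The 80% belongs to a time-averaged difference over a grid that does not correspond to the clamp endpoints, and the plan does not say which window or contrast defines each of them. The fault lies in the power basis and the endpoint definition; it does not show that data will be missing or that the estimate will be biased.

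For an endpoint read once per woman at the end of a step, the power at 15 per group is about 36% two-sided or 49% one-sided, against the stated 80%. With four averaged samples it is roughly 49–58% two-sided by the normal approximation, and about 3 points lower with the t distribution.

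These figures keep the plan's 0.61 and SD of 1 per observation; the four-sample range also rests on the assumed spacing and correlation. If the true SD or difference at steady state differs from these, the power changes too.

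**What to change.** Reconcile item 4 (Visit 3) with item 13, leaving the infusions as they are. In item 13:

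1. Replace the 0–120 min grid with windows at the end of the equilibration and at the end of each insulin step, for example the last 30 min of each, and state the tracer draw times within them.
2. Use these windows as the time factor in the mixed model, and keep earlier samples as descriptive.
3. Name one window-specific group contrast for each primary endpoint.
4. Restate the power for that measure, with its sidedness and the time unit of the AR(1) correlation.

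The work is text plus the timing of draws, which should fit within the roughly 160 mL already planned for the visit. The real cost is candour: fewer repeated values per woman means the restated power will be well below 80%, with a two-sided detectable difference of about 1.0–1.1 SD for a single value. Report that figure rather than enrol more women.

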### SECTION III: RECRUITMENT/CONSENT AND ASSENT PROCEDURES

#### 1. Targeted Enrollment:

- Targeted for enrollment at Yale for this protocol: 32
- If this is a multi-site study, give the total number of subjects targeted across all sites: N/A

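### Sixteen women per group allow for about 6% loss, not the full 5-10% stated: the 10% end leaves about 14 per group and costs 2 to 3 points of power

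*Combined protocol and SAP*

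**What the plan says.** Section I, item 13 gives the power statement: "Group sample sizes of 15 and 15 achieve 80% power to detect a between-group difference of 0.61". The design behind it has seven repeated measurements per woman and an AR(1) covariance, with these settings: "covariance structure when the standard deviation is 1", "the correlation between observations on the same subject is 0.6" and "the alpha level is 0.05". Whether the test is one- or two-sided is not stated.

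The allowance for loss follows directly: "up to 5-10% missing data due to drop out or poor quality data, we will need to enroll a total of 32 subjects", split as 16 per group. Section III, item 1 repeats the total: "Targeted for enrollment at Yale for this protocol: 32". The Research Plan (Section I, item 4) and Subject Population (Section I, item 6) also give 16 per group, so the enrolment number itself is consistent throughout. No section describes replacing women who are lost, or any further allowance.

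**The concern.** The two statements are linked: 15 evaluable women per group carry the power, and 16 enrolled per group are said to protect that 15 over a loss range reaching 10%. One spare woman per group is a thin margin, and it is not obvious that it stretches to 10%. If it does not, the plan claims a power that it would not quite deliver over part of the loss range it names. At stake are the accuracy of the sample size justification and a few points of power.

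**Working it through.** **Inputs, all from Section I, item 13:** 15 evaluable per group; 80% power at that size; difference 0.61 with SD 1; loss 5% to 10%; 16 enrolled per group, 32 in total.

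**1. Reproducing the plan's figure.** The usual inflation is n/(1 − d), with n the evaluable size and d the proportion lost.

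- d = 5%: 15/0.95 = 15.8, rounded up to 16 per group, 32 in total. This is the plan's figure exactly.
- d = 10%: 15/0.90 = 16.7, rounded up to 17 per group, 34 in total.
- The cruder n(1 + d) at 10%: 15 × 1.10 = 16.5, also 17 per group.

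So 32 corresponds to the 5% end of the range. Neither formula gives 16 per group at 10%.

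**2. The loss that 16 per group can absorb.** (16 − 15)/16 = 6.25%; on the total, (32 − 30)/32 = 6.25%.

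**3. What remains at each end.**

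| Loss of whole women | Per group | Total | At least 15 per group? |
|---|---|---|---|
| 5% | 16 × 0.95 = 15.2 | 30.4 | yes |
| 6.25% | 15.0 | 30.0 | yes, just |
| 10% | 16 × 0.90 = 14.4 | 28.8 | no |

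**4. Effect on power, on the plan's own basis.** To isolate the loss allowance, take 80% at 15 per group as given. With two-sided 5% and the normal approximation, the standardised effect at 15 per group is 1.960 + 0.842 = 2.802. It scales with the square root of the group size.

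- 14.4 per group: 2.802 × √(14.4/15) = 2.745; 2.745 − 1.960 = 0.785; power 78.4%.
- 14 per group: 2.802 × √(14/15) = 2.707; 2.707 − 1.960 = 0.747; power 77.2%.

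Sidedness is not stated, so the same step was done for one-sided 5%, starting from 1.645 + 0.842 = 2.487. At 14.4 per group, 2.487 × √(14.4/15) − 1.645 = 0.791, power 78.6%. At 14 per group, 2.487 × √(14/15) − 1.645 = 0.757, power 77.6%. The choice moves the answer by less than half a point.

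**5. The same effect as a detectable difference at 80% power.**

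- 14.4 per group: 0.61 × √(15/14.4) = 0.623 SD.
- 14 per group: 0.61 × √(15/14) = 0.631 SD.

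**The case against.** Four points can fairly be made for the plan.

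- **The plan gives a range, and part of it is covered.** This stands. Everything from 5% to 6.25% is met, and 32 is exactly right at 5%. It would be wrong to say that 16 per group fails the stated range as a whole. But a size said to account for loss up to a limit should hold at that limit, and this one does not hold above 6.25%.
- **Missing data need not mean missing women.** Item 13 names poor-quality data as well as drop-out, and the planned mixed model keeps a woman who has lost only some of her samples. This stands in part: if some of the 10% is scattered samples, more than 14.4 women per group contribute. It does not help with a woman who leaves before the single clamp visit (Visit 3), who contributes no turnover data. The plan itself answers the loss by enrolling more women.
- **The shortfall is one woman per group, in a study that is partly a feasibility pilot.** This stands, and it is why the point is minor.
- **Power does not collapse when a group falls to 14.** This also stands. Ten per cent of 32 is 3.2 women; if three are lost and split two and one, groups of 14 and 15 remain. Their harmonic mean is 2 × 14 × 15/29 = 14.5, for power of about 79% on the two-sided basis above.

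Two stronger readings are tempting and should not be drawn from this point.

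- **That the loss allowance drags power below 70%.** A noncentral t calculation on the mean of seven equally spaced AR(1) measurements gives two-sided power of about 70% at 15 per group and 67% at 14; one-sided it gives about 81% and 78%. The distance from 80% to 70% is already there at 15 per group. It reflects the unstated sidedness and the modelling of the repeated measures, which is a separate question. The loss contributes only the last 3 points.
- **That the design is unlikely to hold its size.** With independent 10% losses, both groups would keep at least 15 with probability of only about 26%. But the plan inflates for expected loss and sets no such criterion; by that test 17 per group would succeed only about 58% of the time.

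**Conclusion.** The statement that 32 women account for loss up to 10% is wrong at its upper end. Sixteen per group preserve 15 per group up to 6.25% loss; 10% would need 17 per group. At 10% loss about 14.4 per group remain, and power falls from the stated 80% to about 78%, or about 77% at 14 per group.

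This rests on two assumptions. First, the loss is of whole women; if part of it is isolated poor samples, the shortfall is smaller. Second, the plan's 80% at 15 per group is taken as given and is not confirmed here. The arithmetic on the allowance needs only the 15, the 16 and the 10%, so it does not depend on how that second question is settled.

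A reader might infer that enrolment must rise to 34 or that the study is materially underpowered because of the allowance. The documents do not support either. The enrolment number is consistent wherever it appears, the lower end of the range is met, and the cost is 2 to 3 points of power. It is a minor error in the justification.

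**What to change.** Keep enrolment at 32 and correct the sentence on loss in Section I, item 13. Suggested content: *Enrolling 32 women (16 per group) allows for the loss of one woman per group, about 6%, while keeping 15 per group. If 10% of women were lost, about 14 per group would remain, and power for a difference of 0.61 SD would be about 77-78%, on the same assumptions that give 80% at 15 per group.*

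Naming the basis matters, because power at 14 per group depends on how the 80% was obtained. If that base calculation is later revised, the 10%-loss figure should be recomputed with it.

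The cost is one sentence and a slightly less favourable stated figure. The enrolment target in Section III, item 1 does not change.

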**SECTION I: RESEARCH PLAN**

1. **Statement of Purpose:** State the scientific aim(s) of the study, or the hypotheses to be tested.

Aim 1: Does lactation improve insulin sensitivity and increase lipolysis in women?

In this Aim, we will assess whether lactation amongst women with a history of GDM will improve whole body insulin sensitivity as well as increase whole body lipid turnover by using hyperinsulinemic-euglycemic clamps combined with [6,6-2H]-glucose and [2H5]-glycerol infusions. These stable, non-radiating isotopes have been used extensively and safely to study the mechanisms of insulin resistance amongst non-pregnant as well as pregnant humans; however, these techniques have not previously been applied to the study of insulin sensitivity during lactation. Our goals will be two-fold: 1) to determine whether lactation induces similar changes in insulin sensitivity in humans as in mice and 2) to pilot the feasibility of performing larger, more detailed metabolic studies in this population of women post-partum.

Aim 2: Retrospective chart review of women with a history of GDM who had an OGTT 6-8 weeks post-partum as part of standard of care at Yale Medicine's Maternal-Fetal Medicine Clinic.

2. **Probable Duration of Project:** State the expected duration of the project, including all follow-up and data analysis activities.

5 years

3. **Background:** Describe the background information that led to the plan for this project. Provide references to support the expectation of obtaining useful scientific data.

Our premise is that lactation protects against the development of Type 2 Diabetes Mellitus (T2D) by mobilizing tissue triglycerides (TGs) and fully reversing the insulin resistance (IR) of pregnancy. A growing body of epidemiological data has indicated that nursing protects against T2D in all women but particularly amongst women with gestational diabetes mellitus (GDM) (1-8). However, no studies have investigated the detailed molecular mechanisms underlying these beneficial effects of lactation. Many studies have

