Nursing and Diabetes Risk. A growing number of epidemiological studies have reported a strong inverse relationship between lactation and the risk of developing T2D (1-8,13-16). The protective effects of lactation hold for all women but are particularly striking in those with a prior history of GDM (2,3,6,8,14). Several large cohort studies have shown that lactation reduced the risk of developing metabolic syndrome and/or T2D and that the degree of risk reduction increased with longer durations of breastfeeding (15,16). These initial cross-sectional studies relied on a self-report of diabetes and did not correct for potentially confounding differences in pre-pregnancy metabolic parameters, weight changes or life-style that might co-segregate with diabetes risk as well as the likelihood of successfully nursing ("reverse causation"). However, more recent prospective studies have addressed these concerns. The SWIFT study demonstrated that increasing lactation intensity and duration decreased the risk of subsequent biochemically defined diabetes by up to 57% over two years post-partum in women with previous GDM (4). Similarly, the 30-year follow up of the Cardia study demonstrated that lactation duration/intensity was associated a graded 25%-47% reduction in subsequent long-term risk of biochemically defined T2D in all women (5). Importantly, both of these studies controlled for confounding factors such as antecedent metabolic or life-style differences and both found that T2D risk reduction was independent of weight loss. Finally, Bajaj and colleagues followed a cohort of women over 3 years and showed that nursing for 12 months or more reduced the risk of prediabetes or T2D by 67% and correlated with persistent improvements in maternal insulin sensitivity (13). Therefore, lactation confers strong, independent, dose-dependent and long-lasting protection against T2D in parous women.

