4. **Research Plan:** Summarize the study design and research procedures using non-technical language that can be readily understood by someone outside the discipline. **Be sure to distinguish between standard of care vs. research procedures when applicable, and include any flowcharts of visits specifying their individual times and lengths.** Describe the setting in which the research will take place.

**Aim 1:** Two groups of 16 women with a history of GDM will be recruited for participation. Group 1 will consist of women who exclusively or mostly breast-fed for at least 4-6 months (< 6 ounces of formula/24 hours at 6-9 weeks of delivery) and who delivered within the past 18 months; Group 2 will consist of women who exclusively or mostly formula-fed (no breastfeeding or < 3 weeks of breastfeeding) and who delivered within the past 18 months.

**Post-partum OGTT visit (standard of care):** 6-8 weeks after delivery, patients from the Yale Medicine’s Maternal-Fetal Medicine Clinic with a history of GDM during pregnancy undergo an OGTT as part of standard of care. At this visit, they may be approached by research staff about participating in this study. If they are interested in participating, they will sign the consent form at this visit and they will then be

asked to complete questionnaires assessing their infant feeding practices, including, but not limited to, overall experience (sources of support, barriers/difficulties faced), frequency/number of feeds, and type of feeds (breastfeeding, expressed breastmilk, formula). Women who are lactating will be given the option to provide us with 2-4 mL of expressed breastmilk, which will be kept frozen and its metabolite content will be studied, including milk lipids, protein, lactose and nucleic acids. The breastmilk will be stored for the duration of the study and will not be shared.

Approximately 8 weeks later, these women will be contacted by research staff and asked about their infant feeding practices. If their feeding practices match the description of Group 1 or Group 2, they will be invited to return for Visit 1, Visit 2 and Visit 3 (described below).

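### Aim 1 compares self-selected feeding groups with no matching and no named covariate, although the protocol faults earlier studies for the same omission

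*Combined protocol and SAP*

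**What the plan says.** Section I, item 1 puts the Aim 1 question causally: "Does lactation improve insulin sensitivity and increase lipolysis in women". It gives two goals: first the effect on insulin sensitivity, then "to pilot the feasibility of performing larger, more detailed metabolic studies in this population of women post-partum".

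Items 4 and 6 form the groups by observed feeding practice, 16 women who exclusively or mostly breast-fed and 16 who exclusively or mostly formula-fed. No randomisation, matching, stratification or propensity method is described.

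Item 13 lists whole body insulin sensitivity, endogenous glucose production and whole body lipid turnover as primary endpoints. On the outcome model it says "Comparisons of repeatedly measured glucose and lipid turnover rates will be made using the mixed model analysis" and "Fixed factors include group and time and their interactions". A random subject effect and an autoregressive matrix deal with within-subject correlation. Patient characteristics are to be compared between groups by t-test, Mann-Whitney or Fisher's exact test. No covariate is named, and item 13 does not clearly say which model serves insulin sensitivity.

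Item 3 (Background) says the initial cross-sectional studies "did not correct for potentially confounding differences in pre-pregnancy metabolic parameters, weight changes or life-style". It describes these as factors "that might co-segregate with diabetes risk as well as the likelihood of successfully nursing". It then credits two later studies: "both of these studies controlled for confounding factors such as antecedent metabolic or life-style differences".

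**The concern.** Whether a woman breast-feeds for months may reflect ability as well as choice, and the Background itself says that nursing success may go with metabolic health before pregnancy. If so, the two groups may have differed in insulin sensitivity before any lactation took place. A model with only group, time and their interaction attributes that difference to lactation. The random subject effect does not help, because it models correlation within a woman and not systematic differences between groups.

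Two things are at stake. The answer to Aim 1's first goal may be biased by an unknown amount in an unknown direction. And if adjustment is decided only after the data are seen, the covariate set can be chosen to suit the result.

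**Working it through.** **Inputs from item 13:** 15 analysed per group, 7 measures, AR(1) correlation 0.6, SD 1, difference 0.61, alpha 0.05 (sidedness not stated).

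**The plan's own figure.** Treat the 7 measures as equally spaced. The variance of a woman's mean is the sum of the 49 correlations divided by 49: 20.71/49 = 0.4227, so SD = 0.650. Noncentrality = 0.61/(0.650 × √(2/15)) = 2.57. With 28 df, power is 80.6% one-sided and 69.9% two-sided. The stated 80% therefore reproduces one-sided. The confounding point does not depend on this.

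**Bias from one unadjusted confounder.** Let d be its between-group imbalance in SD units and r its within-group correlation with the woman's mean outcome. Both are assumed.

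- Bias = r × d × 0.650.
- Noncentrality with no lactation effect = r × d × √(15/2). The outcome SD cancels, so this also holds for an endpoint with one value per woman.
- Rejection rate from the noncentral t, 28 df, two-sided 0.05.

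| r | d | Bias | % of 0.61 | Rejection rate, no true effect |
|---|---|---|---|---|
| 0.3 | 0.3 | 0.059 | 9.6% | 5.7% |
| 0.5 | 0.5 | 0.163 | 26.6% | 10.1% |
| 0.6 | 0.7 | 0.273 | 44.8% | 19.9% |

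**What adjustment achieves** (simulation, 20,000 studies per setting, 15 per group). If the covariate is the only confounder, the adjusted rate is 4.7% to 5.2%. That is true by construction, so a second, independent confounder was then left out (r = 0.3), with BMI at r = 0.5, d = 0.5:

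| Imbalance of omitted confounder | Unadjusted rate | BMI-adjusted rate | Bias left after adjustment |
|---|---|---|---|
| 0.3 SD | 14.3% | 5.7% | 0.056 |
| 0.5 SD | 18.7% | 7.4% | 0.097 |

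**Precision.** The standard error changes by a factor of about √(1 − r²) × √(28/27) × √(1 + 15d²/56). At r = 0.6, d = 0.3 this is 0.80 × 1.018 × 1.012 = 0.82. At r = 0.3, d = 0.7 it is 0.954 × 1.018 × 1.064 = 1.03. The simulation gives the same values.

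**Can the planned tests of characteristics stand in for adjustment?** At 16 per group a two-sided t-test has about 28% power to detect a 0.5 SD imbalance. A non-significant result says little, and a significant one triggers no stated action.

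**Time since delivery.** Group 1 needs 4-6 months of breastfeeding plus 1 month without lactation, so screening starts at 5-7 months. Group 2 women recruited at the clinic OGTT visit are contacted about 8 weeks after a 6-8 week visit, at 14-16 weeks or 3.2-3.7 months. The floors differ by 5 − 3.7 = 1.3 to 7 − 3.2 = 3.8 months. If women are spread evenly from the floor to 18 months (assumed), the means differ by half that, 0.7 to 1.9 months. With SD = (18 − floor)/√12, the pooled SDs are 3.95 and 3.76 months, giving 0.17 to 0.50 SD. Never-nursing women recruited elsewhere have no stated floor.

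**The case against.** **The size is assumed.** True. The documents give no imbalance, correlation or direction. Wider inputs (d = 0.25 to 0.8, r = 0.3 to 0.7) give 8% to 60% of 0.61 and rejection rates of 5.5% to 33.5% (normal approximation). The 0.650 also rests on AR(1) with equal spacing, although the listed times are unequal; compound symmetry gives 0.81, and a mid-case bias of 0.5 × 0.5 × 0.81 = 0.20. Item 13 does not tie 0.61 to an endpoint. The figures show what is possible, not what will occur.

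**The plan is not silent.** The verb in the model sentence need not be exhaustive, and common eligibility limits (age, HbA1C, no prior diabetes, no preeclampsia, no recent dieting) remove some confounding. But BMI is not restricted, and covariates intended but unnamed leave the choice until after the data are seen.

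**It is partly a pilot.** Feasibility is the second goal. The group contrast is the first, and item 13 powers it. This lowers the seriousness but does not remove the point.

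**BMI alone is a thin remedy.** Partly right. It does not cover weight change or life-style. If BMI turns out not to be prognostic (r = 0 to 0.1) and is imbalanced by 0.7 SD, the standard error rises by about 8%. Pre-pregnancy weight recalled up to 18 months after delivery has error: at an assumed reliability of 0.6 to 0.8, the bias left in the mid case is 0.163 × 0.4 to 0.163 × 0.2, or 0.07 to 0.03. That is still well below 0.163.

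**Months since delivery is the only imbalance that follows from the protocol's own rules, yet it goes to a sensitivity analysis.** The even spread is weakly supported, since clinic recruits may be seen soon after contact. The group definition itself partly sets this variable, so it is not a purely pre-lactation characteristic. A sensitivity analysis is a reasonable place for it.

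**Conclusion.** The concern holds. The groups are self-selected, no covariate or matching is named anywhere, and the stated model falls short of the standard that the Background sets for other studies. This should be fixed. It is less serious than it would be in a confirmatory trial, because feasibility is also a goal.

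The omission is certain from the text. Its effect is not: the range of 0.06 to 0.27 rests wholly on the assumed r and d, and at the low end the harm is slight (a rejection rate of 5.7% instead of 5%). The direction cannot be inferred. Adjustment for one pre-pregnancy measure improves on the stated model over most of the range considered, but it does not make the comparison causal.

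**What to change.** Before the data are seen, amend item 13 as follows.

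- Name pre-pregnancy BMI as a covariate in the primary analysis of all three primary endpoints. Add it to the mixed model for turnover rates. State which model serves insulin sensitivity; if there is one value per woman, use ANCOVA. BMI is suggested because it precedes lactation and the Aim 2 chart review already defines it. If the team prefers another pre-pregnancy measure, name it with reasons.
- Report the unadjusted result alongside.
- Put months since delivery, age and GDM treatment in sensitivity analyses.
- Keep current BMI and DXA fat out of the primary model, because lactation may act through them.
- Describe the result as an association with possible residual confounding, including life-style.

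**Cost.** One degree of freedom. The standard error changes by −18% to +3% over the assumed range, or about +8% at worst if BMI is not prognostic. Adding months since delivery raises it a further 2% to 5% (mid case, months imbalance 0.2 to 0.5 SD).

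Pre-pregnancy height and weight must be added to the Aim 1 data, from the medical record where possible to limit recall error. Much of the route exists: the Aim 2 review abstracts them for clinic patients with a 6-8 week OGTT, Visit 1 includes a medical history, Section IV allows collection from the electronic record, and the telephone or email screen (Section III, item 3) asks for height, weight and obstetric history. That screen does not specify pre-pregnancy weight, so the item is mainly new for women who are not clinic patients.
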